8 MONITORING PLAN

The investigators will allow onsite inspection of subjects' source documentation as requested by the sponsor or required by an IRB or regulatory authorities. Monitoring activities may take place at the trial center or any ancillary facility where study conduct takes place. The investigators will provide access to all source documentation and adequate work space. The investigators will be available to the sponsor, IRB or other regulatory authorities to discuss study issues as requested.

Data monitoring will be onsite and occur at the sponsor's discretion but at least annually. An initial monitor visit shall occur as soon as possible after enrollment of the first subject. As needed intermittent monitoring visits will be conducted to compare data entered into the database to all or an unsystematically selected subsample of the subjects' source documents. Monitoring efforts may be expanded if the sample suggests irregularities or for centers with robust enrollment. In all cases, monitor visits shall be conducted if excessive data anomalies are identified.

9 DATA MANAGEMENT AND RECORD RETENTION

Case report forms, paper or electronic, will be used to record satisfying inclusion and exclusion criteria, demographics, medical conditions and co-morbidities, the SF-36 Health Survey, wound assessment and treatment details, wound tracing and characteristics, and subject discontinuation conditions. As needed CRFs will be used to document AEs and protocol deviations. The subject data collected will be entered into a secure database by the clinician or designated staff. Subject data stored in the study database will be identified by the subject number. The unique number will identify the subject and will be included on all case report forms. Authorized representatives of the sponsor (e.g., monitors, auditors, the IRB) will be granted direct access to the subject's original medical records for verification of clinical trial procedures and/or data, as needed, to monitor study conduct. By signing a written ICF, the subject is authorizing such access. The information obtained in this study may be published in scientific journals or presented at scientific meetings, however, the identity of individual participants will not be revealed

without specific written permission by the individual. All records identifying the subject will be kept confidential and, to the extent permitted by the applicable laws and/or regulations, will not be made publicly available.

The investigators will maintain all study records for at least two years following publication of the final study report.

Records to be maintained by the center include but are not limited to:

- IRB correspondence (including approval notifications) related to the clinical protocol, including copies of AE reports and annual or interim reports
- All versions of the IRB-approved clinical protocol and corresponding IRB-approved consent form(s)
- Signed Clinical Trial Agreement, Investigator's Agreement(s), Financial Disclosure(s) and Protocol Agreement Page
- Curriculum vitae and medical license for Investigator(s)
- Training documentation for all study site personnel
- Signed ICFs
- Completed study worksheets (if used), signed and dated by investigator or delegated site personnel
- Source Documents not otherwise located in the subject's medical record
- Monitoring visit communications
- Copies of sponsor notifications of adverse effect information

The sponsor will maintain the following study records:

- IRB correspondence (including approval notifications) related to the clinical protocol;
- All versions of the IRB-approved clinical protocol and corresponding IRB-approved consent form(s)
- Signed Clinical Trial Agreement, Investigator's Agreements and Financial Disclosures
- Curriculum vitae for Investigators
- Training documentation for all study site personnel
- Monitoring visit reports and communications
- Corrective and Preventative Action (CAPA) Plans, if applicable
- AE communications to sites
- Final clinical study report

Binders which may include subject identifying information shall be stored in a secure location at the study center. Subject confidentiality will be protected by the use of unique subject IDs in the electronic database. Subject names will not appear on study reports, publications, or other disclosures of clinical study outcomes.

Investigators will retain the specified records and reports for a minimum of two years after the investigation has been discontinued. Investigators may seek sponsor approval to transfer custody of the records to any other person or entity who will accept responsibility for them.

10 AMENDMENTS TO THE STUDY PLAN

Investigators will not modify, change or otherwise amend the protocol without prior written consent of the sponsor. As applicable, if a protocol amendment substantially alters the scientific validity of the study or affects the subjects' rights, safety, welfare, or their willingness to continue participation in the study, the subject should be re-consented on an updated and approved ICF. New procedures or processes which substantially alter the scientific validity of the study or affects the subjects' rights, safety, welfare, or their willingness to continue participation the study will not be implemented until approval has been granted by the reviewing IRB.

In emergency situations, Investigators shall disregard protocol requirements to ensure the safety, rights, or well-being of subjects.

11 DEVIATIONS TO THE STUDY PLAN

Investigators shall not deviate from the protocol without prior authorization by the sponsor except under emergency situations when necessary to preserve the safety, rights or well-being of subjects. Deviations will be recorded on the appropriate form and include an explanation. Deviations or non-compliances that impact the rights, welfare, or safety of patients shall be reported to the sponsor and IRB as required.

If appropriate, corrective and preventive actions will be discussed by the sponsor, investigator, and/or the IRB to determine a suitable course of action

12 STATEMENT OF COMPLIANCE

This protocol has been developed will be run in accordance with the ethical principles set out in Declaration of Helsinki 2013. Further the study will be run in compliance with ISO 14155 (2nd ed) 2011, CFR Title 21, Part 50 and generally accepted standards of good clinical practice. Both investigators and sponsor will conduct this study in accordance with any applicable local, regional or federal laws and regulations.

Investigators will neither conduct procedures specific to the study nor collect subject data without prior approval of the IRB under whose jurisdiction the conduct of this study falls.

During study conduct, the investigators and the sponsor shall act in accordance with any further requirements as imposed by the IRB or other regulatory agency.

13 SUSPENSION OR TERMINATION OF THE STUDY

The study may be terminated at any time by the sponsor, with no further obligation to follow-up subjects. The study will be closed and the data will be archived according to the appropriate regulations.

14 ADVERSE EVENT AND SAFETY REPORTING

14.1 Definitions

Adverse Event

An adverse event (AE) is any untoward medical occurrence in a subject; it does not necessarily have to have a causal relationship with the device or the procedure. An AE can therefore be any unfavorable and unintended sign (including abnormal laboratory finding), symptom, or condition whether or not considered related to device or procedure.

Serious Adverse Event

A serious AE (SAE) is an AE that leads to 1 of the following conditions:

- Death
- Life-threatening illness or injury
- Serious deterioration in the health of the subject that results in 1 of the following situations:
 - Permanent impairment of a body structure or a body function
 - Medical or surgical intervention to prevent permanent impairment to body structure or body function
 - Inpatient hospitalization or prolongation of existing hospitalization
 - Fetal distress, fetal death, or a congenital abnormality or birth defect

14.2 Reporting of Adverse Events

For the purposes of this study, only events that occur after MIRODERM treatment can be considered AEs. Likewise, reportable AEs will be limited to AEs which are 1) definitely related to, or 2) likely related to, the study wound or treatment. Reportable events include but are not limited to:

- Cellulitis
- Osteomyelitis
- Wound recurrence
- A substantial increase in ulcer size
- Wound infection
- Debridement related AEs

AEs and follow-up information will be reported to the IRB according to the individual IRB's policies

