5 RISK EVALUATION

5.1 Potential Risks to Study Patients

MIRODERM wound matrix is a cleared wound care product and will be used in accordance with approved indications and instructions for use (K140510 and K143426). As an observational, post-market study of a commercialized device for approved indications, the risk to a patient participating in this study is not fundamentally different than the risks this patient would encounter undergoing treatment with a porcine derived biologic wound matrix and not participating in this study. Thus, the only risk unique to this study would be inadvertent disclosure of protected health information.

There are risks, not directly associated with study participation, associated with treatment which may include but are not limited to:

- Sensitivity or allergic reaction to porcine material
- Infection
- Additional tissue damage during sharp debridement
- Cellulitis
- Osteomyelitis

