6 CLINICAL PROTOCOL

6.1 Study design

This is a multi-center post-market, single-arm, prospective follow-up study evaluating outcomes and efficacy of MIRODERM Biological Wound Matrix to treat hard-to-heal DFUs.

Assessment and Roll-in Phase

Patients who suffer from a persistent neuropathic DFU will be recruited from the investigators practice and network, screened for eligibility, invited to participate in the study and provide informed consent.

The subject's demographics, medical history, co-morbidities and wound characteristics will be documented and the subject will complete a SF-36 quality of life questionnaire. Subject will be instructed on proper nutrition.

The DFU will be treated by the investigator with sharp debridement, be traced, photographed, and dressed per standard of care; dressing will be changed daily by the subject. Two tissue sections of at least 2mm will be retained for histological analysis. Subject will be fitted with and instructed on an offloading device. Subjects will return for MIRODERM treatment in two weeks. At the discretion of the investigator, subjects may also be seen 1-week after initial visit; however, this interim visit is not required by the study and will not be documented.

Treatment Phase

On treatment day, subjects will have their wound debrided as necessary, photographed, assessed using the E-Z Graph Wound Assessment System and treated using MIRODERM. They will be asked to return weekly for dressing and wound assessment. After treatment with MIRODERM, subjects will be considered enrolled into the trial. Details of treatment will be documented.

Weekly, for up to 12 weeks, subjects will return, have their wound assessed for closure. As clinically appropriate, they may have their wound debrided and treated using MIRODERM. The wound will be photographed and assessed using the E-Z Graph Wound Assessment System and treatment details will be documented as applicable. The subject will receive a \$25 gift card for attending the follow-up visit.

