6.4 Subject Study Flow Chart

6.5 Assessment and Roll-In Visit (Visit 1; Week 1)

6.5.1 Recruitment and Informed Consent

Male and female patients between 18 and 80 years old (inclusive) who suffer from a persistent neuropathic DFU will be recruited from the investigators practice and network. Patients will have a moderate sized ulcer that has not fully closed during the previous 3 months and who have received at least two attempts using biological solutions. Patients may present with multiple ulcers; however, only a single ulcer per subject will be selected for evaluation in the study protocol.

An assessment of the inclusion and exclusion criteria will be undertaken. All items assessed in the inclusion and exclusion criteria are tests or observations that would be known or obtained as standard of care regardless of the patient's participation in this study. Those patients which appear to be appropriate for the study will be asked to participate and undergo an informed consent procedure. Patients will undergo the informed consent process. At this time, the study procedures, subject expectations and the approved Informed Consent Form (ICF) will be reviewed with the patient. The patient will be given an opportunity to discuss the study with the investigator, including any medical

aspect of their pathology and treatment. The patient will be encouraged to ask questions and will have all of their questions addressed to their satisfaction before deciding whether or not to be in the study.

6.5.1.1 *Signing the Informed Consent Form*

If the patient agrees to participate in the study, the patient will sign the consent form and will be provided with a copy for their records. ***Upon signing the consent form the patient will be considered an active subject in the study but not yet enrolled. The subject will be considered enrolled after treatment with MIRODERM.***

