6.5.6 Wound Tissue Sample

Two tissue sections of at least 2mm will be retained from the debridement material for later analysis.

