6.6.3 Wound assessment and size documentation

Wound will be assessed for gross dimensions and infection. If an infection is present an AE form should be completed and ***the subject will be discontinued from the study.***

The area of the wound will be documented using the E-Z Graph Wound Assessment System and photography.

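### Section 14.2 opens the adverse event window only after MIRODERM is applied; this conflicts with 6.6.3 and 14.1 and leaves roll-in harms, other than infection found at Visit 2, without an AE record

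*Combined protocol and SAP*

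**What the plan says.** Section 14.1 gives a general definition: "An adverse event (AE) is any untoward medical occurrence in a subject", with no restriction on timing. Section 14.2 narrows it for this study: "only events that occur after MIRODERM treatment can be considered AEs". It then limits reporting to events definitely or likely related to the study wound or treatment, and lists debridement-related events among the reportable ones.

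Section 6.5.1 fixes when a person becomes a subject: "Upon signing the consent form the patient will be considered an active subject in the study but not yet enrolled". Enrolment follows the first application. Section 6.1 sets the gap between Visit 1 and that application: "Subjects will return for MIRODERM treatment in two weeks". At Visit 1 the wound is sharply debrided where needed (6.5.7), and 6.5.6 adds: "Two tissue sections of at least 2mm will be retained from the debridement material for later analysis". Section 5.1 includes "Additional tissue damage during sharp debridement" in its list of risks, together with infection, cellulitis and osteomyelitis.

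At Visit 2 the site checks closure (6.6.1), debrides where needed (6.6.2), assesses for infection (6.6.3) and then applies the matrix (6.6.4). The infection instruction opens "If an infection is present an AE form should be completed and" and ends with discontinuation of the subject.

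**The concern.** Two problems follow. The first is a contradiction. A subject found infected at the 6.6.3 step has not yet received MIRODERM. Section 6.6.3 asks for an AE form, 14.2 says the event cannot be an AE, and 14.1 read alone says it is one. With up to 10 centers, the same event may be counted at one site and not at another.

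The second is a gap. Between consent and first application, subjects have a protocol-scheduled debridement and two weeks of daily dressing changes. If 14.2 is followed, harm arising in that time has no place in the AE data. Because 14.1 defines a serious AE as an AE with certain outcomes, an event that cannot be an AE cannot be an SAE either, even if it leads to hospital admission.

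What is at stake is the secondary safety objective in 4.3, which covers both the device and the procedure, and the safeguard in 5.2, which relies on tracking AEs related to the device and the trial. The closure proportion and its confidence interval are not involved.

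**Working it through.** The protocol states no figure on this point to reproduce. The check sets the sections side by side and then measures the length of the uncovered period.

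**Which rule applies to which event**

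- *Infection found at Visit 2 before application.* 14.1: an AE. 14.2: not an AE. 6.6.3: complete an AE form. The three do not agree.
- *Other harm arising between Visit 1 and first application*, such as tissue damage from the Visit 1 debridement. 14.1: an AE. 14.2: not an AE. No section asks for a form.
- *Infection that comes to light before Visit 2.* 6.6.3 applies only at the Treatment Visit. Section 6.1 allows an optional visit one week after Visit 1 but says it is not documented. No AE form is called for at that point.
- *Harm from the Visit 2 debridement that appears after application.* 14.2 dates the event, not its cause, so this is inside the window and reportable.
- *Consented subjects who never receive MIRODERM*, for example those infected at Visit 2 or found closed at Visit 2 under 6.6.1. Under 14.2 they have no AE window at all.

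**What else might record these events.** The discontinuation form (6.10.6) notes when and why a subject leaves, and infection and osteomyelitis are exit reasons in 6.2 and 6.9. It could note an exit. Severity, relatedness, onset and resolution belong to the AE form (6.10.7, 14.3), and a harm that does not lead to exit would not reach the discontinuation form.

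**Length of the uncovered period**

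- Roll-in: 2 weeks (6.1 and the schedule of visits).
- Participation: 9 to 15 weeks (6.2).
- Share of participation: 2/15 = 13.3% to 2/9 = 22.2%.
- Enrolled subjects: 50 to 65 (synopsis). Uncovered time among them: 2 × 50 = 100 to 2 × 65 = 130 subject-weeks.
- Consented but untreated subjects would add to this; the protocol gives no number for them.

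These figures measure time, not missed events. The protocol gives no rate of harm during roll-in, so the number of lost events cannot be computed.

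**The case against.** The best defence is that the window is meant for the device. Section 5.1 describes debridement risk as not directly tied to study participation, section 1 lists debridement as standard care, and the Visit 1 dressing follows standard care. The schedule of visits calls Visit 2 the index procedure and places roll-in before it, so the procedure in 4.3 may not include Visit 1. A device-only window could be defended on that basis. It would still leave 6.6.3 in conflict with 14.2, and it fits poorly with 5.2, which speaks of events related to the trial.

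Several stronger readings are tempting, and the protocol does not support them:

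- A reader might infer that harms of both scheduled debridements are lost because both precede application. That holds for Visit 1 harms that arise during roll-in. For Visit 2 it reaches only harm seen before the matrix goes on.
- A reader might call the two debridements mandatory. Table 1 schedules them, but 6.5.7 and 6.6.2 make them conditional on need.
- A reader might count tissue sampling as a further invasive exposure. Section 6.5.6 takes the sections from debridement material, although 6.10.15 is worded more loosely.
- A reader might infer that every roll-in harm is lost. Infection found at Visit 2 does have a route, through 6.6.3.
- A reader might put the uncovered share at half, from the earliest exit the visit schedule allows (2 weeks of roll-in, 1 to closure, 1 to confirmation: 2/4 = 50%). The protocol states a minimum of 9 weeks, which gives 22%.
- A reader might cite Table 1 as showing the AE form only at follow-up visits. The row's layout in the available text is not reliable enough for that.

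**Conclusion.** The point stands in two parts. Sections 14.1, 14.2 and 6.6.3 contradict one another on an infection found at Visit 2 before first application. In addition, 14.2 as written leaves harms arising in the two-week roll-in without an AE or SAE record, except for infection found at Visit 2. The uncovered period is 13% to 22% of stated participation.

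This rests on the written order of steps at Visit 2 and on 14.2 being applied literally. The effect is confined to the safety objective, and its size in events is unknown. It should be corrected, because it affects both the completeness of the safety data and their consistency across sites.

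**What to change.** Amend 14.2 so that AE recording starts at consent, before the first study debridement, and make 14.1, 6.6.3 and the AE row of Table 1 agree with it. The limit to events related to the wound or treatment can stay. Let the AE form record relatedness to the procedure as well as the device: 6.10.7 names only the device, although the definitions in 14.3 already refer to both.

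Tabulate events in two periods: from consent to first application, with all consented subjects as denominator, and after first application, with all treated subjects as denominator. Device event rates then stay free of pre-treatment events. The number of consented subjects has to be reported, since the planned 50 to 65 counts only those treated.

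Reconciling 14.2 with 6.6.3 alone would remove the contradiction but not the roll-in gap.

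The cost is protocol wording, one table row, one added field on the form, a few more AE forms and one extra summary table. The safety figures may look slightly less favourable.

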14.3 Adverse Event Assessments

All AEs, which are 1) definitely related to, or 2) likely related to, the study ulcer or treatment will be documented on an AE form and assessed by the physician with respect to relatedness and severity.

Each AE record will include a description of the event, date of onset, date of resolution, severity, treatment as applicable, and relationship to study device. Each AE must be recorded separately.

Severity will be assessed using the following definitions:

Mild: Aware of sign or symptom, but easily tolerated

Moderate: Discomfort enough to cause interference with usual activity

Severe: Incapacitating with inability to work or do usual activity

Relationship to the study treatment or the study device will be assessed by the investigator using the following definitions:

Likely: A temporal relationship exists between the event onset and the study procedure or device, and appears with some degree of certainty to be related based on the event symptoms and the nature of the study procedure or device. It cannot be readily explained by the subject's clinical state or concomitant therapies.

Definitely: Strong evidence exists that the study procedure or device caused the AE. There is a temporal relationship between the event onset and the study procedure or device. There is strong mechanistic evidence that the event was caused by the study procedure or device. The subject's clinical state and concomitant therapies have been ruled out as a cause.

15 CLINICAL STUDY ADMINISTRATION AND INVESTIGATORS

15.1 Approval and Agreements

The sponsor and the principal investigator for this clinical research center shall agree to this document and any modifications. A justification for any modifications will be documented. Signing the signature page provided within this document will indicate approval and agreement with the protocol and methods of modifying the protocol.

